4.3.2.1 Atezolizumab and Atezolizumab Placebo

Atezolizumab 840 mg or placebo will be administered by IV infusion on Days 1 and 15 of Cycle 1 and Days 1 and 15 (every 2 weeks) of subsequent cycles (see [Table 2](#) in Section 3.1 for a summary of the treatment regimens).

Administration of atezolizumab will be performed in a setting with medical facilities and staff who are trained to monitor for and respond to medical emergencies. For anaphylaxis precautions, see [Appendix 6](#).

No premedication will be allowed for the first dose of atezolizumab. Patients who experience an infusion-related reaction with the first infusion may receive premedication with antihistamines or antipyretics or analgesics (excluding acetaminophen; see Section [4.4.2](#)) for subsequent infusions.

The initial dose of atezolizumab will be administered over 60 (± 15) minutes. Subsequent infusions will be administered over 30 (± 10) minutes if the previous infusion was tolerated without infusion-associated adverse events, or 60 (± 15) minutes if the patient experienced an infusion-associated adverse event with the previous infusion. Vital signs are to be measured before, as well as during, and after infusions, if clinically indicated, as outlined in Section [4.5.4](#).

Guidelines for medical management of infusion-related reactions are provided in [Appendix 10](#).

No dose modification for atezolizumab is allowed. Guidelines for treatment interruption or discontinuation are provided in Section [5.1.5.4](#) and [Appendix 10](#).

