4.4.1 Permitted Therapy

Patients who use oral contraceptives, hormone-replacement therapy, prophylactic anticoagulation therapy (such as low-molecular-weight heparin at a stable dose level), or other allowed maintenance therapy should continue their use. Male and female patients of reproductive potential should use highly effective means of contraception (see Section 4.1.1).

Patients are permitted to use the following therapies during the study:

- Oral contraceptives
- Hormone-replacement therapy
- Prophylactic or therapeutic anticoagulation therapy (such as warfarin at a stable dose or low-molecular-weight heparin)
- Vaccinations (such as influenza, COVID-19)

Live, attenuated vaccines are not permitted (see Section 4.4.2)

- Megestrol administered as an appetite stimulant
- Inhaled corticosteroids
- Mineralocorticoids
- Low-dose corticosteroids administered for orthostatic hypotension or adrenocortical insufficiency
- Pain medications as indicated, as per standard practice

At the discretion of the investigator, anti-emetic medications, antidiarrheal medications, and may be administered prophylactically per standard local practice before the second and subsequent doses of study treatment. Anti-emetic medications, antidiarrheal

medications, and hematopoietic growth factors are not to be administered prophylactically prior to initiation of study treatment.

Patients requiring treatment for toxicities or for co-existent conditions may be treated as clinically indicated. Planned use of other medications should be discussed with the Medical Monitor.

Premedication with antihistamines may be administered for the second and subsequent atezolizumab infusions only, at the discretion of the investigator.

Patients who experience infusion-associated symptoms may be treated symptomatically with ibuprofen, diphenhydramine, and/or H₂-receptor antagonists (e.g., famotidine, cimetidine), or equivalent medications per local standard practice (acetaminophen is prohibited; see Section 4.4.2). Serious infusion-associated events manifested by dyspnea, hypotension, wheezing, bronchospasm, tachycardia, reduced oxygen saturation, or respiratory distress should be managed with supportive therapies as clinically indicated (e.g., supplemental oxygen and β₂-adrenergic agonists; see Appendix 6).

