4.4.2 Prohibited Therapy

Use of the following concomitant therapies is prohibited as described below:

Prohibited therapies applicable to all patients

- Concomitant therapy intended for the treatment of cancer (including, but not limited to, chemotherapy, hormonal therapy, immunotherapy, radiotherapy for palliative or other purposes, and herbal therapy), whether health authority-approved or experimental, is prohibited for various time periods prior to starting study treatment, depending on the agent (see Section 4.1.2), and during study treatment until disease progression is documented and the patient has discontinued study treatment.
- Investigational therapy is prohibited during the study.
- Anti-emetic medications, antidiarrheal medications, and hematopoietic growth factors are not to be administered prophylactically prior to initiation of study treatment.
- Anti-arrhythmic agents and medications with a risk of torsades de pointes are prohibited within 7 days prior to initiation of study treatment, during study treatment, and for 30 days after the final dose of study treatment.
- Acetaminophen is prohibited within 7 days prior to initiation of study treatment, during study treatment, and for 30 days after the final dose of study treatment, unless the patient has an absolute contraindication to the use of non-steroidal anti-inflammatory drugs (NSAIDs) or aspirin (i.e., severe allergy or reactive airway disease sensitive to NSAIDs or aspirin).

Prohibited therapies applicable to patients receiving atezolizumab (or atezolizumab placebo)

- Denosumab (a RANKL inhibitor) is prohibited during atezolizumab treatment because it could potentially alter the efficacy and safety of atezolizumab. Patients who are receiving denosumab prior to enrollment must be willing and eligible to receive a bisphosphonate instead while in the study.
- Live, attenuated vaccines (e.g., FluMist®) are prohibited within 4 weeks prior to initiation of atezolizumab, during atezolizumab treatment, and for 5 months after the final dose of atezolizumab.
- Systemic immunostimulatory agents (including, but not limited to, interferons and IL-2) are prohibited within 4 weeks or five half-lives of the drug, whichever is longer, prior to initiation of atezolizumab and during atezolizumab treatment because these agents could potentially increase the risk for autoimmune conditions when given in combination with atezolizumab.

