- Metamizole (dipyrone) is prohibited in treating atezolizumab-associated infusion-related reactions because of its potential for causing agranulocytosis.

Prohibited therapies applicable to patients receiving cobimetinib or vemurafenib:

- St. John's wort is prohibited during cobimetinib and vemurafenib treatment and for 2 weeks after the final dose of cobimetinib or vemurafenib (whichever is later)

Patients who require the use of any of the agents listed above will be discontinued from study treatment (unless use is agreed upon in consultation with the Medical Monitor) and followed for safety outcomes for 30 days after their final dose of study treatment or until they receive another anti-cancer therapy, whichever occurs first.

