5.1.1 Risks Associated with Atezolizumab

Atezolizumab has been associated with risks such as the following: infusion-related reactions and immune-mediated hepatitis, pneumonitis, colitis, pancreatitis, diabetes mellitus, hypothyroidism, hyperthyroidism, adrenal insufficiency, hypophysitis, Guillain-Barré syndrome, myasthenic syndrome or myasthenia gravis, *facial paresis*, *myelitis*, meningoencephalitis, myocarditis, *pericardial disorders*, nephritis, myositis, and severe cutaneous adverse reactions. *In addition*, immune-mediated reactions may involve any organ system and lead to hemophagocytic lymphohistiocytosis. Refer to Appendix 10 of the protocol and to Section 6 of the Atezolizumab Investigator's Brochure for a detailed description of anticipated safety risks for atezolizumab.

Guidelines for management of patients who develop specific adverse events associated with atezolizumab, vemurafenib, or cobimetinib are provided in Section 5.1.5.4 (see Table 3), and guidelines for events associated only with atezolizumab are provided in Appendix 10.

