Immune-mediated myocarditis, Grades 2–4	
Permanently discontinue atezolizumab and contact the Medical Monitor.Refer patient to cardiologist.Initiate treatment as per institutional guidelines and consider antiarrhythmic drugs, temporary pacemaker, ECMO, VAD or pericardiocentesis as appropriate.
Immune-mediated pericardial disorders, Grades 2–4	
Initiate treatment with 1–2 mg/kg/day IV methylprednisolone or equivalent and convert to 1–2 mg/kg/day oral prednisone or equivalent upon improvement.

Appendix 10
Risks Associated with Atezolizumab
and Guidelines for Management of Adverse Events Associated
with Atezolizumab (cont.)

	
• If event does not improve within 48 hours after initiating corticosteroids, consider adding an immunosuppressive agent.• If event resolves to Grade 1 or better, taper corticosteroids over \geq 1 month.
--	---

ECMO=extracorporeal membrane oxygenation; VAD=ventricular assist device.

INFUSION-RELATED REACTIONS AND CYTOKINE RELEASE SYNDROME

No premedication is indicated for the administration of Cycle 1 of atezolizumab. However, patients who experience an infusion-related reaction (IRR) or cytokine release syndrome (CRS) with atezolizumab may receive premedication with antihistamines, *antipyretic medications*, and/or analgesics (e.g., acetaminophen) for subsequent infusions. Metamizole (dipyrone) is prohibited in treating atezolizumab-associated IRRs because of its potential for causing agranulocytosis.

IRRs are known to occur with the administration of monoclonal antibodies and have been reported with atezolizumab. These reactions, which are thought to be due to release of cytokines and/or other chemical mediators, occur within 24 hours of atezolizumab administration and are generally mild to moderate in severity.

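### Appendix 10 offers acetaminophen as premedication after an infusion reaction, although Sections 4.3.2.1 and 4.4.2 of the protocol bar it

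*Protocol*

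**What the plan says.** Four parts of the current protocol address acetaminophen.

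- **Appendix 10, Infusion-Related Reactions and Cytokine Release Syndrome.** After either event on atezolizumab, a patient may be premedicated with antihistamines, antipyretics "and/or analgesics (e.g., acetaminophen) for subsequent infusions".
- **Section 4.3.2.1.** After a reaction to the first infusion, a patient may receive "premedication with antihistamines or antipyretics or analgesics (excluding acetaminophen", with a reference to Section 4.4.2, before later infusions.
- **Section 4.4.2, in the list that applies to all patients.** "Acetaminophen is prohibited within 7 days prior to initiation of study treatment, during study treatment", and for 30 days after the final dose, "unless the patient has an absolute contraindication to the use of non-steroidal anti-inflammatory drugs (NSAIDs) or aspirin". The end of the section adds that a patient who needs a listed agent is taken off study treatment "unless use is agreed upon in consultation with the Medical Monitor".
- **Section 4.4.1.** For symptomatic treatment of infusion reactions it repeats that "acetaminophen is prohibited; see Section 4.4.2".

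The body also directs sites to Appendix 10. Section 4.3.2.1 says "Guidelines for medical management of infusion-related reactions are provided in" that appendix. The infusion-reaction row of Table 3 in Section 5.1.5.4 does the same. Section 5.1.1 says that "guidelines for events associated only with atezolizumab are provided in Appendix 10", and the text of Section 5.1.5.4 carries a similar general reference.

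**The concern.** The question a site faces is what may be given before the next infusion once a patient has reacted. Section 4.3.2.1 and Appendix 10 both answer it. One removes acetaminophen from the permitted drugs and the other uses it as the example.

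A site that acts on Appendix 10 in good faith would breach Section 4.4.2 unless one of the two routes applies. That is a protocol deviation to be documented and explained under Section 9.2. A patient judged to require the drug also falls under the discontinuation rule at the end of Section 4.4.2, unless the Medical Monitor agrees to its use.

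A further consequence is only an inference, because the protocol does not say why acetaminophen is barred. Its use could blur the attribution of liver events in the triple combination period. There, ALT, AST and bilirubin determine whether drugs are withheld, reduced or stopped (Section 5.1.5.4, Table 3), and Section 1.5.3 lists hepatotoxicity as an overlapping toxicity of the three drugs.

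**Working it through.** No sample size, alpha or event count enters, so the check is a comparison of text.

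**1. Do the provisions cover the same decision?**

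| Provision | Situation | Acetaminophen |
|---|---|---|
| Appendix 10 | Premedication after an infusion reaction or cytokine release syndrome | Named as an example, without condition |
| Section 4.3.2.1 | Premedication after a reaction to the first infusion | Excluded, with reference to Section 4.4.2 |
| Section 4.4.1 | Symptomatic treatment of an infusion reaction | Prohibited, with reference to Section 4.4.2 |
| Section 4.4.2 | All patients, 7 days before treatment to 30 days after the final dose | Prohibited, with a narrow exception |

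Appendix 10 and Section 4.3.2.1 overlap directly for a reaction to the first infusion. For later reactions and for cytokine release syndrome, Appendix 10 still conflicts with the general prohibition in Section 4.4.2.

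**2. Do the exceptions reconcile the texts?** Section 4.4.2 lifts the bar for an absolute contraindication to NSAIDs or aspirin, and it contemplates use agreed with the Medical Monitor. Appendix 10 imposes neither condition and does not point to Section 4.4.2. They do not.

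**3. Which text is out of line?** Sections 4.3.2.1 and 4.4.1 both defer to the one rule in Section 4.4.2, so the intent is clear and Appendix 10 is the exception. The neighbouring text in Appendix 10 makes a misreading more likely. Its next sentence restates another Section 4.4.2 prohibition, that on metamizole, so a reader sees one analgesic barred and acetaminophen offered. The sentence also contains italic text, which the amendment summary says marks new material, so it was edited in this version and the conflict stayed.

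**4. Is there an order of precedence?** No clause in the supplied protocol ranks the body above its appendices.

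**5. How often are sites sent to Appendix 10 without the exclusion?** The places in the body that refer to it for atezolizumab events are Section 4.3.2.1, Section 5.1.1, the text of Section 5.1.5.4, and the infusion-reaction row of Table 3 in Section 5.1.5.4, which makes 4. Only Section 4.3.2.1 states the exclusion beside the reference: 4 − 1 = 3 without it. Restricted to the two that name infusion reactions, 2 − 1 = 1 lacks it, namely the Table 3 row.

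**The case against.** The strongest reply is that this is an editorial slip. The Appendix 10 wording is permissive, and a site can comply with it fully using an antihistamine or another analgesic. Three body sections agree against one parenthesis, so the working rule is easy to find. Some acetaminophen use would be legitimate under the NSAID or aspirin exception. The liver argument rests on no stated rationale, and two of the four references to Appendix 10 are general ones that would not normally repeat a drug prohibition. No misuse is documented, so the correction could wait for the next amendment without a letter to sites.

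Much of this is fair. The liver argument is an inference and the conclusion does not need it. The count of references does not measure how often a site would act on the wrong text. The Medical Monitor clause, read grammatically, qualifies the discontinuation rule rather than the prohibition, although it plainly envisages agreed use.

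It does not remove the conflict. A permissive sentence that names a prohibited drug still tells the site that the drug is allowed. It sits in the guidance to which Table 3 in Section 5.1.5.4 sends sites for infusion reactions, without a caveat. This is an operative treatment instruction, not background text.

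**Conclusion.** The concern holds, and Appendix 10 is wrong as written. One parenthesis contradicts the prohibition in Section 4.4.2 and its restatement for premedication in Section 4.3.2.1, and no exception or precedence clause resolves it.

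The effect is on safety management and protocol compliance. Its size in patients cannot be stated, because the documents give no infusion-reaction rate. The primary and secondary efficacy analyses, the alpha allocation and power are unaffected. The conclusion rests on taking Section 4.4.2 as the intended rule, which the matching text in Sections 4.3.2.1 and 4.4.1 supports.

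**What to change.** In Appendix 10, replace the parenthesis that gives acetaminophen as an example with the one already used in Section 4.3.2.1, which excludes acetaminophen and refers to Section 4.4.2. The cross-reference keeps both the NSAID or aspirin exception and the Medical Monitor route, since both are in that section. Notify sites of the correction.

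Matching cross-references in Appendix 10 Table 3 and its footnotes c and f are optional: those entries name only drug classes, which are already subject to Section 4.4.2.

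The cost is one parenthesis and a site letter. Concomitant medication is already recorded on its own eCRF (Section 4.4), so neither data collection nor analysis changes.

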The stratification factors will be those used for randomization and will be obtained from the IWRS (geographic region and baseline LDH). Due to the potential risk of over-stratification (Akazawa et al., 1997), if at least one stratum (i.e., a combination of stratification factor levels across geographic region and baseline LDH) has fewer than 10 PFS events across treatment arms, the stratification factor (one of two stratification factors: geographic region and baseline LDH per IWRS) which contains the level with the smallest number of patients will be removed from the stratified analyses. The removal of the stratification factors will continue until there is no stratum with fewer than 10 PFS events. The final set of stratification factors used in stratified analyses will be applied to all endpoints where stratified analyses are planned.

The log-rank test has been the most commonly used method for analyzing survival endpoints under proportional hazards. Due to the potential risk of non-proportional hazards due to delayed treatment effect, the weighted log-rank test will be performed as a sensitivity analysis.

TABLE OF CONTENTS

1.	BACKGROUND	6
2.	STUDY DESIGN	6
2.1	Protocol Synopsis	8
2.2	Endpoints	8
2.2.1	Primary Efficacy Endpoints	8
2.2.2	Secondary Efficacy Endpoints	8
2.2.3	Exploratory Efficacy Endpoints	9
2.2.4	Pharmacokinetic Endpoints	9
2.2.5	Safety Endpoints	9
2.3	Determination of Sample Size	9
2.4	Analysis Timing	10
3.	STUDY CONDUCT	10
3.1	Randomization Issues	10
3.2	Independent Review Facility	11
3.3	Data Monitoring	11
4.	STATISTICAL METHODS	11
4.1	Analysis Populations	11
4.1.1	Randomized Population	11
4.1.2	Safety Population	11
4.1.3	Pharmacokinetic-Evaluable Population	11
4.2	Analysis of Study Conduct	11
4.3	Analysis of Treatment Group Comparability	12
4.4	Efficacy Analyses	12
4.4.1	Primary Efficacy Endpoint	12
4.4.2	Secondary Efficacy Endpoints	13
4.4.2.1	Progression-Free Survival	13
4.4.2.2	Objective Response Rate	13
4.4.2.3	Duration of Response	13
4.4.2.4	Overall Survival	13
4.4.2.5	Patient-Reported Outcomes	14

4.4.3	Exploratory Efficacy Endpoints	15
4.4.3.1	PFS, DOR, and ORR.....	15
4.4.3.2	Patient-Reported Outcomes	15
4.4.3.2.1	Analyses of Study Conduct.....	15
4.4.3.2.2	Visit Score Summary and Change from Baseline.....	15
4.4.3.2.3	Responder Analysis.....	15
4.4.3.2.4	Mixed-Effect Model Repeated Measures Analysis	15
4.4.4	Exploratory [REDACTED]	16
4.4.5	Sensitivity Analyses	16
4.4.5.1	Missing Tumor Assessment.....	16

1. BACKGROUND

This Statistical Analysis Plan (SAP) provides details of the planned analyses and statistical methods for Study CO39262 (IMspire150): a Phase III, double-blinded, randomized, placebo-controlled study of atezolizumab plus cobimetinib and vemurafenib versus placebo plus cobimetinib and vemurafenib in previously untreated *BRAF^{V600}* mutation positive patients with unresectable locally advanced or metastatic melanoma. The background for the study can be found in the study protocol.

It is anticipated that positive results from Study CO39262 will support the submission of filing applications globally for the use of atezolizumab plus cobimetinib and vemurafenib for the treatment of the previously untreated *BRAF^{V600}* mutation positive patients with unresectable locally advanced or metastatic melanoma. For registration purposes, the analyses outlined in this SAP will supersede those specified in the protocol.

2. STUDY DESIGN

[figure not shown]
Study CO39262 is a Phase III, double-blinded, placebo-controlled, randomized, multicenter study designed to evaluate the efficacy, safety, and pharmacokinetics (PK) of atezo+cobi+vem compared with placebo+cobi+vem in patients with previously untreated *BRAF^{V600}* mutation-positive metastatic or unresectable locally advanced melanoma. The primary endpoint of the study is investigator-assessed progression-free survival (PFS).

Approximately 500 patients will be randomized in the study. Patients will be randomized in a 1:1 ratio to one of the two treatment arms:

- Arm A (placebo+cobi+vem): Patients will receive cobimetinib and vemurafenib during a run-in period of 28 days, and then atezolizumab placebo, cobimetinib, and vemurafenib (960 mg twice daily) post run-in.
- Arm B (atezo+cobi+vem): Patients will receive cobimetinib and vemurafenib during a run-in period of 28 days, and then atezolizumab, cobimetinib, and vemurafenib (720 mg twice daily).

The study schema is presented in [Figure 1](#).

Figure 1 Study Schema

21/7=treatment on Days 1–21 followed by no treatment on Days 22–28; BID=twice daily; PS=performance status; QD=once daily; Q2W=every 2 weeks; R=randomization; RECIST v1.1=Response Evaluation Criteria in Solid Tumors, Version 1.1.

- Study treatment will continue until investigator-determined disease progression according to RECIST v1.1 (or subsequent clinical deterioration or confirmed disease progression 4–8 weeks later, for clinically stable patients with a favorable benefit-risk ratio), death, unacceptable toxicity, withdrawal of consent, or pregnancy, whichever occurs first.

Stratification factors are:

- Baseline Lactic Acid Dehydrogenase (LDH) (\leq the upper limit of normal [ULN] vs. $>$ ULN, using central laboratory result);
- Geographic region (North America vs. Europe vs. Australia, New Zealand, and others).

A permuted-block randomization will be applied to ensure a balanced assignment to each treatment arm. Randomization and stratification will be managed through an interactive web-based response system (IWRS).

All patients will be closely monitored for safety and tolerability throughout the study. The National Cancer Institute Common Toxicity Criteria for Adverse Events, Version 4.0 (NCI CTCAE v4.0) will be used to characterize the toxicity profile of the study treatments for all patients. Patients will be assessed for adverse events (AEs) according to the schedule of activities (see [Appendix 2](#)) and as necessary throughout the study.

Tumor assessments will be performed by the investigator and by an independent review committee (IRC) according to RECIST v1.1. Tumor assessments according to [REDACTED] will only be performed by the investigator. All measurable and non-measurable lesions will be documented at screening. Response will be assessed by the investigator at 8- or 12-week intervals until investigator-determined disease progression (according to RECIST v1.1), or death, whichever occurs first. Patients who experience disease progression (RECIST v1.1) must have scans following the

protocol-specified tumor assessment schedule after initial documentation of progression to confirm disease progression. Tumor assessments are to continue according to schedule in patients who discontinue treatment for reasons other than confirmed disease progression. Clinically stable patients who have a favorable benefit-risk ratio should continue on study treatment following radiographic progression per RECIST v1.1. Patients who continue treatment beyond radiographic disease progression will be closely monitored.

Study treatment will continue for all patients until investigator-determined disease progression according to RECIST v1.1 that is confirmed by repeat scans approximately 4-8 weeks later or subsequent clinical deterioration, unacceptable toxicity, death, patient or physician decision to withdraw, or pregnancy, whichever occurs first. Patients who discontinue one study drug may be able to continue other study drugs, per guidelines for management of specific AEs provided in the Protocol Section 5.1. After treatment discontinuation, patients will be followed for disease progression if applicable and followed for survival until death, withdrawal of consent, or loss to follow-up, whichever occurs first. Patients in the control arm cannot crossover to the treatment arm at disease progression. An independent Data Monitoring Committee (IDMC) will be employed to conduct periodic evaluations of safety data.

